APPENDIX 4. *E. COLI* NISSE SENSITIVITY AND RESISTANCE AGAINST COMMON ANTIBIOTICS

E. coli Nisse sensitive to		E. coli Nisse resistant against ^a
Amikacin	Imipenem	Cefsulodin
Amoxicillin/clavulanic acid	Latamoxef	Clindamycin
Ampicillin	Mezlocillin	Erythromycin
Azlocillin	Nitrofurantoin	Metronidazole
Cefaclor	Norfloxacin	Penicillin G
Cefazolin	Pipemidic acid	Quinupristin/dalfopristin
Cefoperazone	Piperacillin	Rifampin
Cefotaxime	Rifampicin	Teicoplanin
Ceftriaxone	Streptomycin	Vancomycin
Cephalothin	Tetracycline	
Chloramphenicol	Ticarcillin	
Ciprofloxacin	Tobramycin	
Doxycycline	Trimethoprim/sulfamethoxazole	
Gentamicin		

Adapted from [Sonnenborn et al 2009](#)

a Like *E. coli* in general, *E. coli* Nisse shows natural resistance against the listed antibiotics. As an isolate from the pre-antibiotic era, *E. coli* Nisse has no acquired resistance, and no antibiotic resistance plasmids are present.

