	
therapeutic doses of anticoagulants, with the exception of patients receiving a preventative dose of low molecular weight heparin. In patients receiving preventative low molecular weight heparin, treatment must be stopped 24 hours before the intratumoral injection and resumed again 24 hours after the injection (Marabelle et al 2018).
 
9. Previous or concurrent malignancy, with the exception of:
a. Adequately treated basal or squamous cell carcinoma, in situ carcinoma of the cervix, or ductal carcinoma in situ of the breast;b. Localized prostate cancer definitively treated with surgery or radiation or stable on hormone therapy;c. Other cancer from which the patient has been disease free for at least 2 years.10. Clinically active central nervous system (CNS) metastases and/or carcinomatous meningitis (treated brain metastases are permitted if radiologically stable for ≥ 28 days prior to the first dose of study treatment).11. Allergy to antibiotics that precludes treatment for infection with E. coli Nissle 1917 (see Appendix 4 for common antibiotics to which E. coli Nissle is sensitive).12. Hepatitis B or C infection(s) unless screening tests indicate a negative viral load, and/or human immunodeficiency virus (HIV) infection unless screening tests indicate a negative or below the limit of quantitation viral load.13. Known active tuberculosis.14. Grade 3 or higher infection according to NCI CTCAE within 28 days prior to initiation of study treatment, including, but not limited to, hospitalization for complications of infection, bacteremia, or severe pneumonia.15. Failure to fully recover from the effects of major surgery. Surgeries that required general anesthesia must be completed > 14 days before the first dose of study drug. Surgery requiring regional/epidural anesthesia must be completed > 72 hours before the first dose of study treatment and participants should be recovered.16. Heart failure of New York Heart Association Class 3 or greater, restrictive cardiomyopathy, or unstable angina or recent myocardial infarction within 3 months prior to the first dose of study treatment.17. Any other medical condition that might confound the results of the study, interfere with the participant's participation, or is not in the best interest of the participant, in the opinion of the treating Investigator.18. Pregnant or breastfeeding or anticipated conception or fathering of children within the projected duration of the study and for 5 months after the last dose of SYNB1891 or atezolizumab. 
Additional exclusion criteria that apply only to Arm 2 study participants are as follows:
 
19. History of immune-mediated AEs on prior PD-1/PD-L1 therapies requiring discontinuation or immunosuppressor therapy, excluding endocrinopathies.

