4.4. Toxicity Management

Participants should receive appropriate supportive care measures as deemed necessary by the treating Investigator.

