Systemic infection	Grade 3 or higher	
Appropriate therapy may include, but is not limited to:
 
 IV fluids NSAIDs Acetaminophen Narcotics Oxygen Pressors Empiric antibiotics Refer to Appendix 4 for EcN-sensitive antibiotics 
Perform local blood and urine cultures and sensitivities.
 
Perform serum qPCR specific for EcN.
	Patients who require systemic antibiotic treatment should postpone dosing with SYNB1891 for the duration of the antibiotic regimen and for 5 half-lives after the last dose of antibiotics and until the patient is apyretic.
Local injection site reactions (may include associated AEs, e.g., abscess, infection, ulceration or necrosis, or severe tissue damage)	Grade 3 or higher	
Consider surgical intervention as needed in addition to and in accordance with local standard of care, which may include, but is not limited to:
 
 NSAIDs Acetaminophen Antibiotics 	Permanently discontinue study treatment.

Abbreviations: AE = adverse event; CTCAE = Common Terminology Criteria for Adverse Events; *EcN* = *E. coli* Nissle; IL = interleukin; IV = intravenous; NCI = National Cancer Institute; NSAID = nonsteroidal anti-inflammatory drug; qPCR = quantitative polymerase chain reaction

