10. Clinically active central nervous system (CNS) metastases and/or carcinomatous meningitis (treated brain metastases are permitted if radiologically stable for \geq 28 days prior to the first dose of study treatment).

11. Allergy to antibiotics that precludes treatment for infection with *E. coli* Nissle 1917 (see [Appendix 4](#) for common antibiotics to which *E. coli* Nissle is sensitive).
12. Hepatitis B or C infection(s) unless screening tests indicate a negative viral load, and/or human immunodeficiency virus (HIV) infection unless screening tests indicate a negative or below the limit of quantitation viral load.
13. Known active tuberculosis.
14. Grade 3 or higher infection according to NCI CTCAE within 28 days prior to initiation of study treatment, including, but not limited to, hospitalization for complications of infection, bacteremia, or severe pneumonia.
15. Failure to fully recover from the effects of major surgery. Surgeries that required general anesthesia must be completed > 14 days before the first dose of study drug. Surgery requiring regional/epidural anesthesia must be completed > 72 hours before the first dose of study treatment and participants should be recovered.
16. Heart failure of New York Heart Association Class 3 or greater, restrictive cardiomyopathy, or unstable angina or recent myocardial infarction within 3 months prior to the first dose of study treatment.
17. Any other medical condition that might confound the results of the study, interfere with the participant's participation, or is not in the best interest of the participant, in the opinion of the treating Investigator.
18. Pregnant or breastfeeding or anticipated conception or fathering of children within the projected duration of the study and for 5 months after the last dose of SYNB1891 or atezolizumab.

Additional exclusion criteria that apply only to Arm 2 study participants are as follows:

19. History of immune-mediated AEs on prior PD-1/PD-L1 therapies requiring discontinuation or immunosuppressor therapy, excluding endocrinopathies.
20. Active or history of underlying autoimmune disease or immune deficiency, including, but not limited to, myasthenia gravis, myositis, autoimmune hepatitis, systemic lupus erythematosus, rheumatoid arthritis, inflammatory bowel disease, antiphospholipid antibody syndrome, Wegener granulomatosis, Sjögren syndrome, Guillain-Barré syndrome, or multiple sclerosis, with the following exceptions:

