7.2.2.1. Monitoring for Signs and Symptoms of Infection

If clinical presentation warrants, including but not limited to cases in which patients develop persistent (> 24 hours) fever or a change in vital signs suggestive of clinical infection resulting from a study treatment or procedure, then blood and urine cultures (performed and analyzed locally) will be performed and weight will be recorded.

If a patient is treated for systemic infection such that blood culture tubes are drawn locally, an additional blood culture tube should be drawn for analysis for the presence of SYNB1891, if possible. For this purpose, patients will be provided with an identification card containing study contact information (see Central Laboratory manual for collection, shipping, and other processes).

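### Protocol Appendix 4 lists one antibiotic in both columns: rifampicin as sensitive and rifampin as resistant (minor)

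*Protocol*

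**What the plan says.** Appendix 4 of the Protocol is a table of common antibiotics, adapted from a cited review. Two columns give the agents to which *E. coli* Nissle is sensitive, and a third gives those to which it is resistant. Rifampicin is in the sensitive list and rifampin is in the resistant list. Footnote a, attached to the resistant column, says that the strain "shows natural resistance against the listed antibiotics" and has no acquired resistance. It makes no exception for any agent and does not mention the pair.

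Two operative parts of the Protocol depend on this table:

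- **Exclusion criterion 11** (Synopsis and Section 5.2.1.2) begins "Allergy to antibiotics that precludes treatment for infection with" the strain. It directs the reader to the appendix for agents that work: "Nissle 1917 (see Appendix 4 for common antibiotics to which" the strain is sensitive.
- **Table 2 in Section 4.4.1**, in the row for systemic infection of Grade 3 or higher, says "Refer to Appendix 4 for" antibiotics active against the strain.

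The same row of Table 2 is permissive about therapy ("Appropriate therapy may include, but is not limited to" the measures listed) and adds "Perform local blood and urine cultures and sensitivities". Section 4.4 is also permissive: "Participants should receive appropriate supportive care measures as deemed necessary by the treating Investigator". Section 7.2.2.1 says that, when a systemic infection is treated and cultures are drawn locally, "an additional blood culture tube should be drawn for analysis for the presence of SYNB1891, if possible".

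**The concern.** Rifampicin and rifampin are two nonproprietary names for the same drug. The documents do not say so, but it is ordinary nomenclature. The strain cannot be both sensitive and naturally resistant to one drug without some qualification, such as a different assay or breakpoint, and the table gives none.

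The two possible errors do not carry the same risk. If the resistant entry is wrong, sites lose one option among many. If the sensitive entry is wrong, a site could rely on it for an empiric choice before culture results are back, in a first-in-human trial of an injected live bacterium. Section 4.3.1 holds SYNB1891 for the whole antibiotic course plus 5 half-lives, so an ineffective first choice could also lengthen the interruption. In principle the sensitive entry could also bear on an eligibility decision under exclusion 11.

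**Working it through.** No figure in the plan needs to be reproduced. The check is a reading of the table, followed by a count.

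**1. Is the placement real, or an artefact of reading the PDF?** Each column is alphabetical. Rifampicin stands between piperacillin and streptomycin in the second sensitive column. Rifampin stands between quinupristin/dalfopristin and teicoplanin in the resistant column. A cell that had slipped across columns would normally break the order. Both names are where the table's author put them.

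**2. Does anything reconcile the two entries?**

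| Place | What it offers | Does it settle the point? |
|---|---|---|
| Appendix 4, body | No assay, concentration or breakpoint | No |
| Appendix 4, footnote a | Asserts natural resistance to whatever is in the resistant column | No; it repeats the column's content |
| Section 2.2 | Antibiotic resistance genes used in engineering were removed | No; this is not natural resistance |
| Section 2.2.1 | Sensitivity to a broad panel of antibiotics | No; no agent is named |
| Rest of Protocol and SAP | Neither name appears | No |

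**3. Counts, from Appendix 4.**

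- Sensitive entries: 14 (first column) + 13 (second column) = 27.
- Resistant entries: 9.
- All entries: 27 + 9 = 36. Distinct drugs: 36 − 1 = 35.
- Share in doubt: 1/27 = 3.7% of sensitive entries, 1/9 = 11.1% of resistant entries, 1/35 = 2.9% of drugs.
- Uncontradicted sensitive agents: 27 − 1 = 26.

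**4. Could the entry decide eligibility under exclusion 11?** By ordinary drug classes, 14 of the 26 are beta-lactams: amoxicillin/clavulanic acid, ampicillin, azlocillin, cefaclor, cefazolin, cefoperazone, cefotaxime, ceftriaxone, cephalothin, imipenem, latamoxef, mezlocillin, piperacillin and ticarcillin. The other 26 − 14 = 12 are amikacin, gentamicin, streptomycin, tobramycin, ciprofloxacin, norfloxacin, pipemidic acid, doxycycline, tetracycline, chloramphenicol, nitrofurantoin and trimethoprim/sulfamethoxazole. A patient allergic to every listed beta-lactam would still have 12 listed agents that nothing contradicts.

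**5. The table after correction.** If the drug is resistant: 26 + 9 = 35 entries. If it is sensitive: 27 + 8 = 35 entries. Either way there is one entry per drug.

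**The case against.** The conflict itself is hard to dispute. The case on the other side concerns its weight and the remedy.

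- **Almost nothing follows from it.** For the entry to decide eligibility, allergy would have to rule out the other 26 agents. For treatment, Table 2 is a recommendation, it is open-ended, and it asks for cultures, sensitivities and serum qPCR in the same row. SYNB1891 is a dual auxotroph that did not grow without supplementation (Section 2.2.1). All of this stands, and it is why the point is minor. It does not make the table right.
- **The footnote is evidence for resistance.** It states natural resistance to the listed agents, and rifampin is listed. But if the entry were in the wrong column, the footnote would still read the same. It cannot settle which entry is wrong.
- **The cited source may explain both entries**, for example as results from separate test panels. That is possible and cannot be excluded here. Sites work from the Protocol, however, and the Protocol carries no explanation.
- **Removing the sensitive entry first amounts to choosing a side and makes two changes where one would do.** If the source can be checked at once, a single correction is better. If it cannot, interim removal is a precaution and does not decide the question: a false sensitive entry is worse than one unlisted agent.
- **The percentages measure no risk.** Agreed. They describe only how much of the table is affected.

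**Conclusion.** The concern holds as a minor internal inconsistency. One drug of 35 is classified both ways, in a safety reference table that an exclusion criterion and an infection-management guideline both use. The conclusion rests on one assumption from outside the documents, that the two names denote one drug. It does not depend on which classification is correct, and the documents do not show that.

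The practical effect is small, with 26 uncontradicted agents left. The DLT definitions, the mTPI table, the sample size and the planned analyses are untouched. This does not mean that trial outcomes are independent of how an infection is treated: a Cycle 2 delay of more than 2 weeks or a Grade 5 event (Section 4.2.4), or a related death (Section 4.5), could depend on it.

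**What to change.** Take rifampicin out of the sensitive column for now, leaving 26 sensitive and 9 resistant entries, so that it is not relied on for exclusion 11 or Table 2. Then check the source from which Appendix 4 was adapted, or the sponsor's own susceptibility data, and list the drug once, under one name, in the column that the evidence supports. If the check can be done straight away, make both changes in one step.

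The work is a look-up and a one-row edit. A stand-alone amendment would be out of proportion. Section 12.2 allows any amendment to be implemented only once the IRB's approval letter has reached the sponsor, Section 12.3 requires submission to the FDA first, and Section 10.8 requires prior IRB approval where patient risk is affected. A clarification memo to sites would be quicker, but the documents do not describe one. The sponsor would have to decide whether a memo is enough or the correction waits for the next planned amendment.

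If the drug turns out to be sensitive, the cost of interim removal is that 1 of 27 usable agents (3.7%) was unlisted for a time. Sample size and analysis are not affected.

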DOOR	duration of response
ECG	electrocardiogram
ECHO	echocardiogram
EcN	Escherichia coli Nissle 1917
eCRF	electronic case report form
EDC	electronic data capture
EOT	End of Treatment
°F	degree(s) Fahrenheit
FDA	Food and Drug Administration
FNA	fine needle aspirate
g	gram(s)
GCP	Good Clinical Practice
geoCV	geometric coefficient of variation
GLP	Good Laboratory Practice
h	hour
HIV	human immunodeficiency virus
ICH	International Council for Harmonisation of Technical Requirements for Pharmaceuticals for Human Use

Abbreviation or Specialist Term	Explanation
ICF	Informed consent form
IgG1	immunoglobulin G1
IFN	interferon
IL	interleukin
IL1Ra	interleukin 1 receptor agonist
IR	immune response
IRB	Institutional Review Board
iRECIST	immune-related Response Evaluation Criteria in Solid Tumors
i.t.	intratumoral
IV	intravenous
L	liter(s)
LVEF	left ventricular ejection fraction
LYRIC	Lymphoma Response to Immunomodulatory Therapy Criteria
m ²	meter(s) squared
mAb	monoclonal antibody
MedDRA	Medical Dictionary for Regulatory Activities
mg	milligram(s)
min	minute(s)
mL	milliliter(s)
mM	millimolar(s)
MTD	maximum tolerated dose
mTPI	modified toxicity probability interval
MUGA	multi-gated acquisition scan
NCI	National Cancer Institute
NE	not evaluable
ORR	objective response rate
OS	overall survival
PD	progressive disease
PET	positron emission tomography
PFS	progression free survival
PK	pharmacokinetic(s)
PR	partial response
PT	preferred term
Q3W	every 3 weeks

Abbreviation or Specialist Term	Explanation
qPCR	quantitative polymerase chain reaction
QTcF	QT interval corrected for heart rate using Fridericia's formula
RP2D	recommended phase 2 dose
RECIST	Response Evaluation Criteria in Solid Tumors
SAE	serious adverse event
SAP	statistical analysis plan
SD	stable disease
SOC	system organ class
STING	STimulator of INterferon Genes
TEAE	Treatment Emergent Adverse Events
TIL	tumor-infiltrating lymphocytes
TNF α	tumor necrosis factor α
TPP	time to progression
WHO-DD	World Health Organization Drug Dictionary

I. Introduction

A. Background

While immunotherapies have become the standard-of-care for numerous cancers, significant unmet medical need persists primarily for the 55-87% of patients failing to respond to checkpoint inhibitors (CPIs). However, one emerging biomarker correlated with response is intratumoral (i.t.) immune cell infiltration (Zou et al 2016) where patients with higher levels of immune cell infiltration prior to therapy exhibit higher response rates to CPIs. Combination therapies seek to expand response rates by driving higher levels of immune cell infiltration into tumors, triggering antigen-presenting cell (APC) activation and promoting productive tumor-antigen presentation to effector T cells (Zou et al 2016). To this end, an interest in innate immune agonists has emerged.

SYNB1891 is a strain of modified live probiotic bacterium (*Escherichia coli* [E. coli] Nissle 1917) (EcN) programmed as a live immuno-biotherapeutic agent designed to treat patients with cancer. From nonclinical studies, SYNB1891 demonstrated significant antitumor control and the ability to deliver a STING agonist. Activation of STING results in the induction of Type I IFNs, like IFN β , and in the context of cancer can trigger the initiation of antitumor immunity through the activation of APCs and the presentation of tumor-antigens to effector T cells (Corrales et al 2015).

Atezolizumab is a humanized immunoglobulin G1 (IgG1) monoclonal antibody. It is currently approved in the United States as a single agent or as a component of combination therapy for several indications. Atezolizumab has demonstrated antitumor activity in both nonclinical models and cancer patients and is being investigated as a potential therapy in a wide variety of malignancies in addition to the approved indications.

This rationale lends support to the investigation of i.t. administration of SYNB1891 to activate the innate immune system which subsequently promotes the initiation of antitumor immune responses in the injected tumor, as well as the demonstration of long-term immunological memory. As the first clinical study of SYNB1891, study SYNB1891-CP-001 aims to determine the maximum tolerated dose (MTD) as a monotherapy and recommended Phase 2 dose (RP2D) of SYNB1891 in combination with atezolizumab in patients with advanced/metastatic solid tumors or lymphoma.

The protocol for Study SYNB1891-CP-001 describes the general approach to analysis of data from the study. This analysis plan describes additional detail needed to complete such an analysis. Appendix 5 provides the table of contents for summary tables, listings and figures based on this analysis plan.

B. Protocol and Amendment History

This Statistical Analysis Plan (SAP) is based on version 4.0 of Protocol Amendment SYNB1891-CP-001.

Version	Approval Date	Salient Changes, if any*
Protocol version 4.0	27 July 2020	
Protocol version 3.0	27 May 2020	
Protocol version 2.0	11 February 2020	
Protocol version 1.0	27 June 2019	

* Changes expected to require accommodation in analysis plan.

This SAP will govern the analysis of data from this study. Any deviations from the analysis plan will be documented as such in the study report.

II. Protocol Objectives and Analysis Endpoints

The overall objective is to evaluate the safety and tolerability of escalating doses of i.t. injections of SYNB1891 to determine the single-agent MTD as monotherapy and the RP2D in combination with atezolizumab.

Objective	Endpoints
Primary: 
Incidence of dose-limiting toxicities (DLTs): Percentage of patients who experience a DLT	
The number and percentage of patients who experience a DLT through the end of Cycle 1
Secondary: 
Nature, incidence, and severity of all adverse events (AEs) and serious adverse events (SAEs) according to the National Cancer Institute (NCI) Common Terminology Criteria for Adverse Events (CTCAE), version 5.0Objective response rate (ORR) as determined by the Response Evaluation Criteria in Solid Tumors, version 1.1 (RECIST 1.1) (Eisenhauer et al 2009), immune-related RECIST (iRECIST) (Seymour et al 2017), and/or the Lymphoma Response to Immunomodulatory Therapy Criteria (LYRIC) (Cheson et al 2016).	
The number and frequency of AEs and SAEs.The number and frequency of AEs and SAEs under each severity category.Objective response rate (complete response and partial response) per RECIST, iRECIST and LYRIC at any time on studyEvaluations of the SYNB1891-injected tumor(s), including tumor size, tumor response, etc.

Exploratory: 
Duration of response or time to progression for evaluated tumors as determined by RECIST 1.1, iRECIST, and/or LYRICPharmacodynamic response biomarkers including tumor infiltrating lymphocytes (TIL) characterization, immunomodulatory cytokine gene expression and IFNβ responsive genes to be monitored in proximal and (if available) distal lesion biopsies at baseline and on study; systemic pharmacodynamic effects will be evaluated by assessment of changes in serum cytokine levels (including, but not limited to, tumor necrosis factor α [TNFα], interleukin [IL] 2, IL-4, IL-6, IL-8, IL-10, IL-12p70, IL-13, IL1β, IL 1 receptor antagonist [IL1RA], IL 2 receptor alpha [IL2R α], and IFNγ) at baseline and while on studyKinetics of SYNB1891 within the injected tumor will be assessed by quantitative polymerase chain reaction (qPCR) from predose (baseline) to Cycle 1 Day 8 from a fine needle aspirate (FNA); systemic kinetics of SYNB1891 will be monitored by qPCR from blood at 6 hours and 24 hours postdose in Cycle 1	
Time to progression (TTP); progression free survival (PFS); overall survival (OS); time to best response; duration of response (DOR)Assessment of changes in biomarker and serum cytokine parameters at baseline and while on study.Assessment of qPCR at each visit and changes from baseline
--	--

III. Study Design

A. Design Overview

This Phase 1, open-label, multicenter, 2-arm study will follow the design in Appendix 1.

Patients enrolled to Arm 1 may receive up to four 21-day cycles, of SYNB1891 monotherapy escalated until the target DLT range is determined. On Days 1, 8, and 15 of Cycle 1 and Day 1 of Cycles 2 through 4, patients will receive an i.t. injection of SYNB1891 into an eligible lesion. If the initial eligible lesion undergoes complete regression and is no longer injectable (at the discretion of the Investigator), a subsequent eligible lesion (until no more eligible lesions remain) may be injected. The starting dose of SYNB1891 in the first cohort of Arm 1 will be 1×10^6 live cells and will be increased in approximately 3-fold increments in subsequent cohorts until MTD determination. A mTPI dose-finding design (Ji et al 2013, see Appendix 2) with a target DLT rate of approximately 30% will be applied for dose escalation and confirmation to determine the MTD/RP2D. In Arm 1, predetermined dose levels of 1×10^6 , $3 \times$

10^6 , 1×10^7 , 3×10^7 , 1×10^8 , 3×10^8 , and 1×10^9 live cells will be explored independently. A de-escalation dose of 3×10^5 live cells is available if the starting dose is deemed not tolerable. All dose escalation and de-escalation decisions will be based on the occurrence of DLTs at a given dose during Cycle 1 and will be made jointly by the Investigators and the Sponsor. If the initial eligible lesion undergoes complete regression and is no longer injectable, subsequent eligible lesions (until no more eligible lesions remain) may be injected. At the end of Cycle 4, patients may receive additional cycles of SYNB1891; for details refer to protocol section 4. The dose selected as achieving the target DLT range will be considered the MTD.

After determination of the MTD in Arm 1, dosing will begin in Arm 2 at a 10-fold lower dose than the Arm 1 MTD and will be increased in approximately 3-fold increments in subsequent cohorts until RP2D determination. Patients will follow the same four 21-day cycles schedule as Arm 1 and SYNB1891 will be administered by i.t. injection into an eligible lesion on Days 1, 8, and 15 of Cycle 1 and Day 1 of Cycles 2 through 4. In addition, atezolizumab will be administered in accordance with its recommended dose and schedule (1200 mg IV Q3W) on Day 1 of each of the 4 planned cycles. Combination doses will not be escalated above the SYNB1891 single-agent MTD established in Arm 1. On days when atezolizumab and SYNB1891 are both administered, SYNB1891 will be administered first, followed by at least 1 hour of observation prior to the atezolizumab infusion. Patients in Arm 2 who do not have progressive disease at the end of Cycle 4 on combination therapy may receive additional cycles of SYNB1891 and atezolizumab for up to 24 months, details refer to protocol section 4.

Once the RP2D of Arm 2 is determined, up to 20 additional patients may be enrolled in the RP2D cohort to fully characterize the safety profile of SYNB1891 in combination with atezolizumab.

B. Study Population

This study comprises patients with advanced/metastatic solid tumors or lymphoma. Patients will be eligible for enrollment regardless of gender or race/ethnicity. Additional inclusion and exclusion criteria can be found in protocol section 5.

C. Sample Size Predictions

No formal sample size calculations were performed, as the study is primarily designed for empirical evaluation of safety and tolerability in patients with advanced solid tumors or lymphoma. The anticipated sample size is approximately 70 patients, which provides for 4 to 7 dose-finding cohorts in Arm 1, 1 to 5 cohorts in Arm 2, and replacement of 1 patient per cohort, as well up to 20 additional patients enrolled at the RP2D in Arm 2 to fully characterize the

safety profile of SYNB1891 in combination with atezolizumab. Additional cohorts may be required in either arm to determine the MTD/RP2D.

D. Assessment Schedule

The maximum time of study participation for a patient is up to 26 months, including the screening period (up to 28 days), treatment administration period (up to 24 months), and safety follow-up period (30 ± 5 days after the last dose). The various assessments that will be conducted during this study are summarized in Appendix 3.

IV. Interventions

A. Clinical Trial Material

SYNB1891 investigational drug product is formulated in buffer composed of 15% glycerol, 5% trehalose, 10 mM Tris at pH 7.5. SYNB1891 is packaged aseptically into AT-closed vials at a volume of 0.6 mL and labeled for clinical study use. The manufactured SYNB1891 drug product has a concentration of 1×10^{11} live cells/mL.

Atezolizumab is supplied by the manufacturer as a sterile liquid in a single-use, 20-mL glass vial and labeled and shipped to each investigational site. Atezolizumab (1200 mg/vial) is prepared in accordance with local prescribing information and administered as an IV infusion at a dose of 1200 mg Q3W.

The protocol provides additional product details in Section 6.

B. Study Procedures

Before recruitment of patients into the study, written Institutional Review Board (IRB) approval of the protocol, informed consent, and any additional patient information must be obtained. For both study arms, screening procedures must be performed to determine eligibility for enrollment within 28 days prior to the first dose of study treatment.

Patients will undergo safety assessment, efficacy assessment, pharmacodynamic assessments and follow-up assessment.

In safety assessment, patients will provide information on medical history, adverse event, vital signs, physical examination, laboratory measurements, Electrocardiograms, and Multi-gated Acquisition Scan or Echocardiogram.

Efficacy will be assessed in the SYNB1891-injected lesion(s) and an overall response of up to 5 noninjected target lesions determined using appropriate

imaging at screening and every 2 cycles on study (i.e., at the beginning of every odd-numbered cycle) for the duration of the treatment period and at the EOT visit (unless imaging has been performed within 8 weeks prior to the EOT visit).

Tumor biopsies and blood samples for qPCR will be collected during the first 24-hour period of Cycle 1 and will be analyzed to assess the pharmacodynamics of circulating SYNB1891.

All patients will attend a Safety Follow-up visit 30 ± 5 days after the last dose of study treatment. Within 14 days after the last dose of study treatment (or premature treatment discontinuation), an EOT visit will be performed.

The protocol provides additional details in Section 7.

V. General Analytical Considerations

A. Data Sources

All reported study data will be recorded on the electronic case report forms (eCRF) using Medidata Rave. During the data collection process, automated quality assurance programs will be used to identify missing data, out-of-range data, and other data inconsistencies. External data will be provided by external vendors. Central lab cytokines data from serum will come from Q2 Solutions; qPCR data from injected tumor FNA, tumor biopsies and blood samples will come from QPS; microbiology data will come from Laboratories ITNL Microbiology Studies (IHMA).

B. Definition of Baseline

Baseline is defined as the last measurement taken prior to the first dose of study medication. The average of the predose results will be considered as the baseline value for vital signs taken at different timepoints on the same day predose.

C. Missing Data

Due to the dose escalation design of the study, no imputation of missing values will be done for the primary objective. When relevant, sections below will address how missing data will be handled for the particular analysis.

Partial dates are allowed on the eCRF for prior disease therapy start and stop dates, adverse event (AE) onset and resolution dates, concomitant medication start and stop dates, and concomitant procedure, procedure dates. An entry for the year is required in the eCRF system for each of these dates. Only the month and day may be entered as unknown. Dates from these forms will be reported in listings as collected. Every effort will be made to query missing dates.

For records with missing AE onset date, the following procedure will be employed for use in determining whether the AE is treatment emergent:

- AE onset dates with missing day and non-missing month will be assumed to occur on the first day of the non-missing month, except for AEs occurring in the month and year of first dosing, in which case the date will be imputed using the date of first dosing.
- AE onset dates with missing day and month will be assumed to occur on the first day of the non-missing year (ie, January 1), except for AEs occurring in the year of first dosing, in which case the date will be imputed using the date of the first dosing.
- AEs that are not ongoing and have a resolution date with missing day and non-missing month, they will be assumed to occur on the last day of the month, except when the end of study date or date of death is prior to the last day of the month. The date will be imputed as end of study date, or death date, whichever happens the earliest.
- AEs that are not ongoing and have a resolution date with end date month missing, the imputed end date should be set to the last day of the year 31DECYYYY, except when the end of study date or date of death is prior to the last day of the year. The date will be imputed as end of study date, or death date, whichever happens the earliest.

For records with a missing medication start and/or stop date, the following procedure will be employed for use in determining whether the medication is prior or concomitant:

- Medication start dates with a missing day and non-missing month will be assumed to occur on the first day of the non-missing month, except for medications occurring in the month of first dosing, in which case the date will be the date of first dosing.
- Medication start dates with missing day and month will be assumed to occur on the first day of the non-missing year (ie, January 1), except for medications occurring in the year of first dosing, in which case the date will be the date of first dosing.
- Medications that are not ongoing and have a medication stop date with a missing day and non-missing month will be assumed to occur on the last day of the non-missing month.
- Medications that are not ongoing and have a medication stop date with missing day and month will be assumed to occur on the last day of the non-missing year (i.e., December 31).

For records with a missing procedure date, the following procedure will be employed for use in determining whether the procedure is prior or concomitant:

- Procedure dates with a missing day and non-missing month will be assumed to occur on the first day of the non-missing month, except for

- procedures occurring in the month of first dosing, in which case the date will be the date of first dosing.
- Procedure dates with missing day and month will be assumed to occur on the first day of the non-missing year (i.e., January 1), except for procedures occurring in the year of first dosing, in which case the date will be the date of first dosing.

For records with a missing disease progression date from prior therapy, the following procedure will be employed for use in analyzing time to event endpoints:

- If the disease progression date is completely missing OR only the year is available, set as missing.
- If both year and month of disease progression date from are available and only day is missing, the date of disease progression will be imputed by the last day of the month.

For records with a partial death date, the following procedure will be employed for use in deriving time to event variables.

- The death date will be imputed by the earliest possible date that is not contradicting with any other available data in the database.

All other data will be reported as they are collected. No imputation methods will be used to replace missing data unless otherwise stated in this document.

D. Interim Analyses

This is a single-arm, open-label study, so interim analyses may be performed as the study progresses.

Details of analysis will follow each section described in this SAP, may including the following components:

- Disposition
- Protocol deviations
- Baseline characteristics: demographics, disease history, medical history, concomitant medication/procedure
- Key components from efficacy analysis
- Key components from safety analysis
- PK and pharmacodynamic data (as available)

E. Analysis Populations

1. Safety Population

The safety population includes participants who were enrolled, allocated to treatment, and received at least one dose of investigational product.

2. Efficacy Population

The efficacy population includes participants who received study drug and had an on-treatment response assessment (including “Not Evaluable”) or who discontinued study before any response assessment performed due to disease progression.

